5.4.2.2.1. Definition of Endpoints

5.4.2.2.1.1. Psoriasis Area and Severity Index (PASI)

Details refer to section [5.3.1.1.](#)

5.4.2.2.1.2. Investigator's Global Assessment (IGA)

Details refer to section [5.4.1.2.1.2.](#)

5.4.2.2.1.3. Psoriasis Symptom and Sign Diary (PSSD)

Details refer to section [5.4.1.2.1.4.](#)

5.4.2.2.2. Estimand for Secondary Endpoints

Same analysis strategies as the main estimand of the study 77242113PSO2001 specified in section [5.4.1.2.2.](#) will be used

- ICEs 1 - 2 in the primary estimand (definitions in Section [5.3.1.2.1.](#)) will be handled with the Composite Strategy.
- ICE 3 in the primary estimand will be handled with Treatment Policy strategy

5.4.2.2.3. Analysis Methods

Unless otherwise specified, the analysis population will be based on FAS defined in Section [4.2](#), more specifically, randomized participants who received at least one dose of study intervention in the originating study (77242113PSO2001) for participants initially randomized to JNJ-77242113, and participants who crossed over and received JNJ-77242113 for participants initially randomized to placebo.

Similar to the secondary endpoint efficacy analyses for study 77242113PSO2001, the endpoints will be summarized by intervention group. Simple descriptive statistics, such as n, mean, SD, median, IQ range, minimum and maximum for continuous variables and counts and percentages for discrete variables will be used to summarize most data. No formal statistical testing will be performed. The baseline data from the originating study (77242113PSO2001) will be used to calculate the change-from-baseline-related endpoints.

Binary Endpoints

The analysis strategy for ICEs and missing data will be handled in the same manner as the primary estimand for the primary endpoint of 77242113PSO2002 (Section [5.3.2.3](#)). The proportions of participants who achieved a clinical response and its 95% confidence interval for the above binary secondary efficacy endpoints will be provided for each intervention group.

Continous Endpoints

Unless otherwise specified, the analyses for continuous secondary endpoints at Week 36 and other time points will be based on the strategies specified in Section [5.4.1.3.2](#) to handle ICEs and missing data.

- ICEs 1 - 2 in the primary estimand (definitions in Section 5.3.1.2.1) will be handled with the composite strategy. Participants experiencing ICEs 1-2 will have a zero change (or zero improvement) from baseline assigned from that point onward.
- ICE 3 in the primary estimand (definitions in Section 5.3.1.2.1) will be handled by the treatment policy strategy. The analysis will be performed using observed data regardless of intercurrent events. For participants experiencing multiple ICEs, ICE 2 will override an ICE 3.
- Missing data will not be imputed after applying the rules for intercurrent events.

For continuous endpoints, the change from baseline at each week will be analyzed using a restricted maximum likelihood-based mixed model for repeated measures with fixed effects for treatment, visit, stratification factor of baseline weight category (≤ 90 kg, >90 kg), baseline value, baseline value by week interaction, baseline weight category by week interaction, and the treatment-by-week interaction. An unrestricted (UN) variance-covariance matrix for repeated measures within a participant will be used. If the model with unstructured covariance structure does not converge, alternative covariance structures will be tried in the following order, with the first structure that converges being used in the analysis: heterogeneous Toeplitz, standard Toeplitz, and autoregressive of order 1. Least Square means (LSmeans) and their corresponding 95% confidence interval will be provided, and no statistical testing will be performed.

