5.3.1.2.1. Primary Estimand (Estimand 1)

The primary estimand, based on the above primary objective, is defined by the following 5 attributes which assess the treatment effects not only based on the variable measurements, but also based on intercurrent events:

Study intervention:

- JNJ77242113 25 mg QD, 50 mg QD, 25 mg BID, 100 mg QD, and 100 mg BID.
- Placebo

Population: adult participants with moderate to severe psoriasis

Variable/endpoint: Binary response variable, where a responder is defined as a participant achieving a PASI75 response at Week 16. A participant with an intercurrent event in categories 1-2 defined below will be considered as a non-responder.

Intercurrent Events (ICEs) and their corresponding strategies.

ICEs	Analysis Strategy for Addressing Intercurrent Events
1. Discontinuation of study intervention due to lack of efficacy, or an AE of worsening of psoriasis prior to Week 16	Composite Strategy: Participants with these intercurrent event are considered as non-responders. The occurrence of these intercurrent events is captured in the variable definition.

2. Initiation of a protocol-prohibited medication or therapy during the study that could improve psoriasis prior to Week 16	
3. Discontinuation of study intervention for reasons other than ICE 1	Treatment Policy: observed data will be used regardless of whether or not this intercurrent event had occurred.

- ICEs 1 and 2 will be handled by the composite strategy, where the occurrence of the ICE will be incorporated into the variable definition. Participants experiencing ICE 1 or 2 will be considered not to have achieved the primary endpoint.

- ICE 3 will be handled using the treatment policy strategy regardless of the intercurrent event.

Note: For participants experiencing multiple ICEs, ICE 2 will override ICE 3.

A list of Participants who experienced ICEs 1-3 will be provided.

Population level summary: Difference in the proportions of participants achieving a PASI 75 responses at Week 16 between the treatment groups.

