5.3.2.2. Estimands

5.3.2.2.1. Primary Estimand

In this primary estimand, the components that are different from the definition of the primary estimand of study 77242113PSO2001 are the intervention attribute, Variable/endpoint, and Population level summary; and all other components are the same as the primary estimand as specified in Section 5.3.1.2.1.

Study intervention: JNJ-77242113 25 mg QD, 50 mg QD, 25 mg BID, 100 mg QD, 100 mg BID, and placebo → 100 mg QD

Variable/endpoint: Binary response variable, where a responder is defined as a participant achieving a PASI75 response at Week 36. A participant with an intercurrent event in categories 1-2 defined in Section 5.3.1.2.1 will be considered as a non-responder.

Population level summary: Descriptive summary statistics for the proportions of participants achieving a PASI 75 responses at Week 36 for each of the treatment groups.

Note: If the Week 0 visit for study 77242113PSO2002 takes place on a different day as the Week 16 visit of study 77242113PSO2001 with a gap greater than 4 weeks, the participants are allowed to take medications specified in 77242113PSO2002 that could improve psoriasis after 4 weeks from the Week 16 visit of study 77242113PSO2001 and before entering the study of 77242113PSO2002; ICE 2 specified in Section 5.3.1.2.1 will not be applied in this situation.

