5.3.2.3. Analysis Methods for Primary Estimand

The primary efficacy analysis for study 77242113PSO2002 will be based on the FAS defined in Section 4.2. Since there is no control arm (placebo), in this primary analysis, only the proportion of participants who achieve a PASI75 response and its 95% confidence interval at Week 36 will be summarized for each intervention group.

The data handling method specified in Section 5.3.1.2.3 will be applied. More specifically, participants with ICEs 1-2 before Week 36 will be considered as PASI75 non-responders at Week 36. Participants with ICE 3, observed PASI data after this ICE will be utilized in the analysis. After accounting for the ICEs for the primary estimand, participants with the missing data of the primary endpoint at Week 36 will be considered as non-responders.

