5.4.1.2.2. Main Estimands for Secondary Endpoints

The secondary endpoints will be analyzed similarly as the primary estimand described in section 5.3.1.2.1 as the main estimand. The main estimand will be considered for both binary and continuous secondary endpoints. The analysis strategy for ICEs and missing data will be handled in the same manner as the primary estimand for the primary endpoint

- ICEs 1-2: Composite strategy
- ICE 3: Treatment policy strategy

The study intervention and population are the same as the primary estimand.

BINARY ENDPOINTS

Variables and Population-level Summary: Difference in the proportions of participants achieving a clinical response (eg, PASI 90 responses at Week 16) between the treatment groups. The variables and population level summaries for the other secondary binary endpoints are similarly described.

CONTINUOUS ENDPOINTS

Variable (Endpoint): change from baseline to Week 16 (change = Week 16 - baseline).

- Participants who have intercurrent events in categories 1, 2 through Week 16 will have a zero change from baseline assigned from the point of the ICE, regardless of the observed data.

Population-level summary: LSMean difference in change from baseline in eg, change from baseline in total PASI score at Week 16 between JNJ-77242113 treatment groups and the placebo group. The variables and population -level summaries for the other secondary continuous endpoints are similarly described.

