5.5.2.2. Analysis Methods

For exploratory efficacy analyses of the study 77242113PSO2002, efficacy data from the combined 77242113PSO2001 and 77242113PSO2002 studies will be included (FAS (Section 4.2)). More specifically, efficacy data will be summarized over time from Week 1 of study 77242113PSO2001 through Week 52 (Week 36 of the 77242113PSO2002 study) by treatment groups.

For overtime efficacy analyses that combines the 77242113PSO2001 and 77242113PSO2002 studies, Week 4 visit of the study 77242113PSO2002 will be aligned as Week 20 for the combined study and will be denoted as “Week 20 (LTE Week 4)” in the summary table; similar notation will be applied for the subsequent visits of the study 77242113PSO2002.

Similar to the exploratory endpoints in 77242113PSO2001, the analysis strategy for ICEs and missing data for the exploratory analyses for 77242113PSO2002 will be handled in the same manner as the main estimand for the secondary analyses of the study 77242113PSO2001 (5.4.1.2.2, section 5.4.1.3.1 and section 5.4.1.3.2).

Since 77242113PSO2002 is a LTE study following the originating study 77242113PSO2001 and no formal hypothesis testing. Simple descriptive summary statistics, such as n, mean, standard deviation (SD), median, interquartile range, minimum, and maximum for continuous variables, and counts and percentages for discrete variables will be used to summarize most data. The baseline data from the originating study (77242113PSO2001) will be used to calculate the change-from-baseline-related endpoints.

For exploratory continuous endpoints, same MMRM model approach specified in Section 5.4.1.3.2 will be used for the change from baseline at each week. Least Square means (LSmeans) and their corresponding 95% confidence interval will be provided, and no statistical testing will be performed.

Additionally, graphical data displays may also be used to summarize the over time data if applicable.

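### The intercurrent-event window in the extension is inconsistent: Week 36 for the primary and binary secondary analyses, but Week 16, carried over unchanged, for the continuous secondary and all exploratory endpoints

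*SAP*

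**What the plan says.** SAP 5.3.1.2.1 builds the time limit into the events themselves. ICE 1 is "Discontinuation of study intervention due to lack of efficacy, or an AE of worsening of psoriasis prior to Week 16" and ICE 2 is "Initiation of a protocol-prohibited medication or therapy during the study that could improve psoriasis prior to Week 16". ICE 3, handled by treatment policy, is the remainder, with no time limit: "Discontinuation of study intervention for reasons other than ICE 1". For continuous endpoints, SAP 5.4.1.2.2 repeats the limit: "Participants who have intercurrent events in categories 1, 2 through Week 16 will have a zero change from baseline".

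For the extension, the estimand text in SAP 5.3.2.2.1 points back to the same definitions: "A participant with an intercurrent event in categories 1-2 defined in Section 5.3.1.2.1 will be considered as a non-responder". The analysis section that follows, SAP 5.3.2.3, then changes the window: "participants with ICEs 1-2 before Week 36 will be considered as PASI75 non-responders at Week 36". In SAP 5.4.2.2.3 the binary secondary endpoints cite 5.3.2.3 and so take the Week 36 window.

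The other extension endpoints do not cite 5.3.2.3. For the continuous secondary endpoints, SAP 5.4.2.2.3 says "ICEs 1 - 2 in the primary estimand (definitions in Section 5.3.1.2.1) will be handled with the composite strategy", and 5.4.2.2.2 cites the same definitions. For the exploratory endpoints, SAP 5.5.2.2 says that the strategy for intercurrent events and missing data "will be handled in the same manner as the main estimand for the secondary analyses of the study 77242113PSO2001".

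**The concern.** A time limit that suits a 16-week study has been carried into a 36-week extension. SAP 5.3.2.3 shows that a new window was needed, because it supplies one for the primary endpoint. The continuous secondary and exploratory sections have no such override.

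Two things are at stake. The first is what the estimates mean. A change score or response rate that uses values observed after prohibited psoriasis therapy partly describes that therapy. The second is consistency within one report. PASI 75 at extension Week 36 is the primary endpoint, and it is also the last point of the over-time PASI table in SAP 5.5.2.2.1. If the two follow different rules, one visit in one analysis set has two PASI 75 rates. Likewise, at extension Week 36 the same participant could be a failure for PASI 90 and yet contribute a full observed improvement to the change in PASI total score.

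**Working it through.** The plan states no figure on this point, and SAP 3.2 gives no formal sample size for the extension, so there is nothing to reproduce. The check is a trace of the cross-references, followed by an illustration of size.

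**Trace of the window**

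| Extension endpoint | Sections followed | Window reached |
|---|---|---|
| Primary, PASI 75 at Week 36 | 5.3.2.2.1 to 5.3.1.2.1, overridden in 5.3.2.3 | before Week 36 |
| Binary secondary | 5.4.2.2.3 to 5.3.2.3 | before Week 36 |
| Continuous secondary | 5.4.2.2.2 and 5.4.2.2.3 to 5.3.1.2.1, 5.4.1.2.2 and 5.4.1.3.2 | Week 16, no override |
| Exploratory, continuous | 5.5.2.2 to 5.4.1.2.2 and 5.4.1.3.2 | Week 16, no override |
| Exploratory, binary | 5.5.2.2 to 5.4.1.3.1 to 5.3.1.2.3 | Week 16, no override |

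**Literal result for events in the extension.** A stop for lack of efficacy or worsening psoriasis comes too late to be ICE 1. It is therefore a stop for a reason other than ICE 1 as defined, which makes it ICE 3, and observed data are used. Prohibited therapy started in the extension comes too late to be ICE 2 and fits no category, so observed data are again used. Reading the limit as extension Week 16 would not cure this, because events between extension Weeks 16 and 36 would still be missed.

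**Same visit, two rules.** SAP 5.1.3.2 aligns extension Week 4 with combined Week 20, so extension Week 36 is Week 16 + 36 = Week 52. Both tables use the full analysis set of SAP 4.2.

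**Who is affected.** For binary exploratory endpoints, the chain ends in SAP 5.3.1.2.3, where missing data count as non-response. Participants who stop and leave therefore remain failures, and only those with observed data after the event can change the rate. For continuous endpoints, missing values are not imputed and the repeated-measures model handles them.

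**Size, as an illustration.** The documents give no extension event rate. Assume an arm of 40, the planned group size of the originating study, with everyone still contributing.

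- Response rate, per affected participant observed as a responder: 1/40 = 2.5 percentage points.
- Raw mean PASI change, per participant with baseline PASI 12 (the entry minimum) who is fully cleared: (12 − 0)/40 = 0.30 points.

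For an arm as a whole, let f be the share with such an event and with observed data afterwards.

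- Shift in mean = f × proportional improvement × baseline PASI. With f of 5% to 15%, improvement of 50% to 90% and baseline PASI of 12 to 20, the range runs from 0.05 × 0.50 × 12 = 0.30 to 0.15 × 0.90 × 20 = 2.70 points.
- Shift in rate = f × response rate among those affected. With 25% to 75% responding, the range runs from 0.05 × 0.25 = 1.25 to 0.15 × 0.75 = 11.25 percentage points, or 0.5 to 4.5 of 40 participants.

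All these inputs are assumed, except that 12 is the eligibility threshold and 20 is the SAP's baseline PASI subgroup cut. The planned estimates include least-squares means from the repeated-measures model, so the raw-mean figures are approximate.

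**The case against.** The strongest reply is that nobody intended this. Three pieces of text support that.

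- SAP 5.3.2.2.1 switches ICE 2 off for certain medication taken in a long gap between the two studies. That exception is needed only if ICE 2 otherwise applies after Week 16.
- SAP 5.4.2.2.3 says that its continuous rule covers Week 36 and other time points, and it assigns zero change from the event onward. The cited rule in 5.4.1.3.2 adds no Week 16 cap of its own.
- SAP 5.3.2.3 itself uses the ICE 1 and 2 labels for events up to Week 36.

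This stands as evidence of intent. A reader might infer that the SAP has decided not to count extension failures for these endpoints, and the documents do not support that: no section says so. But intent does not settle the derivation. The onward clause says how long the zero value lasts, not which events trigger it. The gap exception appears only under the primary estimand. Two programmers could build different datasets from this text.

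Three other inferences should be resisted. One is that the error always favours the drug. ICE 1 includes stopping for worsening psoriasis, and a participant observed above baseline would make the arm's mean look worse than an assigned zero would. Another is that 0.3 PASI points per participant is a minimum; it assumes full clearance, and partial improvement gives less. The third is that the extension's primary endpoint is free of the problem. Its estimand text carries the same import, and only its analysis section corrects it.

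It is also fair to say that the amount of data observed after stopping depends on the extension protocol, which is not among the documents.

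**Conclusion.** The window is wrong as written, which is more than a missing detail: the cited rules state a limit, and it is the wrong one for a 36-week extension. It conflicts with the primary analysis of PASI 75 at the same visit and with the apparent intent of SAP 5.3.2.2.1 and 5.4.2.2.3.

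The consequence is confined to descriptive estimates and their comparability across tables. SAP 2.2 sets no hypothesis for the extension and there is no control arm, so no error rate is involved and nothing in 77242113PSO2001 changes. How large the discrepancy becomes depends on how many participants have an extension event and are still assessed afterwards, which the documents do not say. The per-participant figures above hold only under the assumed arm of 40. For continuous endpoints the direction is not fixed, although effective prohibited therapy would push estimates towards the drug.

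**What to change.** State one rule for 77242113PSO2002 in SAP 5.4.2.2.2, in the continuous part of 5.4.2.2.3 and in 5.5.2.2. For consistency, put it in the estimand text of 5.3.2.2.1 as well. ICE 1 and ICE 2 are the same event types as in the originating study, counted up to the visit being analysed, through extension Week 36. Non-response or zero change is assigned from the event onward.

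The same rule should say that the gap exception to ICE 2 in 5.3.2.2.1 applies in the same way to every extension endpoint. Without that sentence, widening the window would create a new mismatch, because gap medication would count as ICE 2 for some endpoints and not for the primary.

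The cost is a sentence or two of SAP text. The event derivation is already needed for the primary endpoint and can be reused by visit. Some extension estimates may come out slightly less favourable.

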5.5. Exploratory Endpoint(s) Analysis

5.5.1. Study 77242113PSO2001

Objective: To characterize additional efficacy of JNJ-77242113 versus placebo for the treatment of regional psoriasis and to explore treatment satisfaction after using JNJ-77242113 in participants with moderate-to-severe plaque psoriasis

In addition to the primary and secondary efficacy endpoints, the analyses for exploratory efficacy endpoints (including the over time summaries through Week 16) will be performed. These efficacy endpoints include the endpoints related to

- PASI
- IGA
- BSA
- Patient-reported Outcomes

PSSD

DLQI

Patient-Reported Outcomes Measurement Information System-29 (PROMIS-29)

Genital Psoriasis Sexual Frequency Questionnaire (GenPs-SFQ)

Patient Global Impression- Severity (PGI-S) and Change (PGI-C)

In addition, to characterize additional efficacy of JNJ-77242113 versus placebo for the treatment of regional psoriasis and to explore treatment satisfaction after using JNJ-77242113 in participants with moderate-to-severe plaque psoriasis, the following exploratory endpoints will be evaluated at Week 16 and over time.

- To characterize additional efficacy of JNJ-77242113 versus placebo for the treatment of regional psoriasis:
 - Nail Psoriasis Area and Severity Index (NAPSI)
 - Fingernail Physician's Global Assessment (f-PGA)
 - Static Physician's Global Assessment of Genitalia (sPGA-G)
 - Physician's Global Assessment of Hands and/or Feet (hf-PGA)
 - Scalp Specific Investigator Global Assessment (ss-IGA)
- To explore treatment satisfaction after using JNJ-77242113 in participants with moderate-to-severe plaque psoriasis
 - Treatment Satisfaction Questionnaire for Medications (TSQM-9 domains)

5.5.1.1. Endpoint Definitions

5.5.1.1.1. Psoriasis Area and Severity Index (PASI)

Details refer to section [5.3.1.1](#)

5.5.1.1.2. Investigator's Global Assessment (IGA)

Details refer to section [5.4.1.2.1.2](#)

5.5.1.1.3. Body Surface Area (BSA)

Details refer to section [5.4.1.2.1.3](#)

5.5.1.1.4. Psoriasis Symptom and Sign Diary (PSSD)

Details refer to section [5.4.1.2.1.4](#)

5.5.1.1.5. Dermatological Life Quality Index (DLQI)

Details refer to section [5.4.1.2.1.5](#)

5.5.1.1.6. Patient-Reported Outcomes Measurement Information System-29 (PROMIS-29)

Details refer to section [5.4.1.2.1.6](#)

5.5.1.1.7. Genital Psoriasis Sexual Frequency Questionnaire (GenPs-SFQ)

The GenPs-SFQ is a 2-item patient reported survey used to assess the impact of genital psoriasis on the frequency of sexual activity in the last 7-days. Item 1 assesses overall frequency of sexual activity in the last 7-days (none/zero, once, or two or more times) and item 2 assesses how frequently genital psoriasis symptoms have limited the frequency of sexual activity in the last 7-days (never [0], rarely [1], sometimes [2], often [3], or always [4]).

The analyses for GenPs-SFQ item 2 will be based on participants randomized at Week 0 with a GenPs-SFQ item 2 score ≥ 2 at baseline.

5.5.1.1.8. Patient Global Impression- Severity (PGI-S) and Change (PGI-C)

Interpreting meaningful change in scores on PRO instruments is an important step in evaluating results and is included in FDA guidelines. The methods for interpreting meaningful change have evolved over time and various approaches exist. Anchor-based methods are often preferred. Anchor-based methods link scores on the PRO to an external criterion that identifies participants who have experienced an important change in their condition. The PGI-S and PGI-C will be used as anchors, external criteria, to determine meaningful change in scores for other PROs in this population. The PGI-S contains 1 question on how the participant would currently rate severity of disease in the past 7 days, with responses ranging from 1="None" to 5="Very severe." The PGI-C contains 1 question on how the participant would rate the change from their first treatment in this study. The response options are presented on a 7-point scale from 1="A lot better now" to 7="A lot worse now."

